5.4 Treatment blinding

This is a double-blind randomized treatment trial. Subjects, investigators, site personnel, and persons performing the assessments will remain blinded to treatment assignment from the time of randomization until the Week 52 database lock and analyses are completed, using the following methods:

1. Randomization data are kept strictly confidential until the time of unblinding and will not be accessible by anyone else involved in the study with the exception of the bioanalyst
2. The identity of the treatments will be concealed up to the Week 52 database lock and analyses are completed by the use of study treatments in the form of PFS for s.c. injection, filled with secukinumab or placebo that are identical in appearance.

Unblinding of treatment dose or original randomized treatment assignment before the Week 52 database lock and analyses are completed will only occur in the case of subject emergencies (see [Section 5.5.12](#)).

The hsCRP results from samples collected during the treatment period will be revealed only after the Week 52 database lock and analyses are completed.

The X-Ray interpretations performed by central Imaging Contract Research Organization (CRO) personnel will not be disclosed to investigators, site personnel, subjects and monitors during the trial.

The primary efficacy analysis will be performed when the database is locked (after all subjects have completed Week 24 assessments). Summary results may be shared internally and externally; however, individual unblinded subject data will not be disclosed. Data analysts will not remain blinded after the Week 24 database lock. A final database lock will occur when all subjects have completed the study.

5.5 Treating the subject

5.5.1 Subject numbering

Each subject is uniquely identified by a Subject Number which is composed by the site number assigned by Novartis and a sequential number assigned by the investigator. Once assigned to a subject, the Subject Number will not be reused.

Upon signing the informed consent form, the subject is assigned the next sequential number by the investigator. The investigator or his/her staff will contact the IRT and provide the requested identifying information for the subject to register them into the IRT. The site should select the case report form (CRF) book with a matching Subject Number from the electronic data capture (EDC) system to enter data.

If the subject fails to be treated for any reason, the IRT must be notified within 2 days that the subject was not treated. The reason for not being treated will be entered on the Screening Epoch Study Disposition CRF.

Subjects may be re-screened once and will receive a new Subject Number after they have been re-consented. Subjects who are mis-randomized cannot be re-screened.

5.5.2 Dispensing the investigational treatment

Each study site will be supplied by Novartis with investigational treatment in packaging of identical appearance.

The investigational treatment packaging has a 2-part label. A unique randomization number is printed on each part of this label which corresponds to placebo or active treatment. Investigator staff will identify the investigational treatment package(s) to dispense to the subject by contacting the IRT and obtaining the medication number(s). Immediately before dispensing the package to the subject, investigator staff will detach the outer part of the label from the packaging and affix it to the source document (Drug Label Form) for that subject's unique subject number.

5.5.3 Handling of study treatment

Investigational treatment must be received by a designated person at the study site, handled and stored safely and properly, and kept in a secured location to which only the investigator and designees have access. Upon receipt, all investigational treatment should be stored according to the instructions specified on the labels. Clinical supplies are to be dispensed only in accordance with the protocol. Technical complaints are to be reported to the respective Novartis Country Pharma Organization (CPO) Quality Assurance.

Medication labels will be in the local language and comply with the legal requirements of each country. They will include storage conditions for the investigational treatment but no information about the subject except for the medication number.

The PFS (150 mg active/placebo) sealed in their outer box must be stored in a access controlled/locked refrigerator between 2°C and 8°C (36°F and 46°F) (Do Not Freeze) and protected from light. They must be carefully controlled in accordance with regulations governing investigational medicinal products and local regulations.

If the subject will be self-administering treatment at home (after Week 52), the investigator should ensure the subject can store the medication according to these conditions before allowing the subject to self-administer at home.

The investigator must maintain an accurate record of the shipment and dispensing of investigational treatment in a Drug Accountability Log. Monitoring of drug accountability will be performed by monitors during site visits or remotely and at the completion of the trial. Subjects will be asked to return all unused investigational treatment and packaging at the next site visit, at the end of the study or at the time of discontinuation of investigational treatment.

At the conclusion of the study, and as appropriate during the course of the study, the investigator will return all partly used and unused investigational treatment, packaging, drug labels, and a copy of the completed drug accountability log to the Novartis as instructed.

Destruction of the unused drug should be done according to local requirements and after approval by the Novartis Clinical Team.

5.5.4 Instructions for prescribing and taking study treatment

Study treatment (150 mg secukinumab and placebo) will be administered by s.c. PFSs throughout the study. Administration of study treatment will occur at the study site through Week 52. Administration of study treatment must occur after the study assessments for the visit have been completed. After Week 52, subjects will be allowed to self-administer the study treatment at home during the optional visits in which there are no scheduled assessments at the site (see Home Administration in [Table 6-2](#) below).

The PFS with the ready-to-use study treatment solution will be provided by the site staff to the subject. Detailed instructions on the self-administration of the study treatment will be described in the Instructions For Use (IFU) and provided to each subject.

At the BSL visit, subjects will be instructed by the site staff, utilizing the IFU, on how to self-inject using a PFS. Subjects will be asked to raise questions, if they have any, and then to proceed with self-injection. At the Week 1 visit, subjects will be asked to refer to the IFU and to proceed directly with self-injection of the study drug (i.e., no prior retraining) for the remainder of the trial. However, if the subject is not comfortable self-injecting the study treatment, then the site staff may administer it for the subject.

All study treatment kits assigned to the subject during the study will be recorded in the IRT.

The first study treatment administration will occur at the BSL/randomization visit only after eligibility criteria have been confirmed, all study scheduled BSL assessments have been performed and the scheduled blood samples have been drawn.

At each subsequent visit, all study assessments, including the completion of Patient Reported Outcomes (PROs), (as applicable per [Table 6-1](#) and [Table 6-2](#)), should be completed prior to the self-injection of study treatment.

The investigator should promote compliance by instructing the subject to attend the study visits as scheduled and by stating that compliance is necessary for the subject's safety and the validity

of the study. The subject should be instructed to contact the investigator if he/she is unable for any reason to attend a study visit as scheduled or if he/she is unable for any reason to take the study treatment as prescribed.

5.5.4.1 Subcutaneous administration with PFSs

Secukinumab solution for subcutaneous injection (150 mg in 1.0 mL active/placebo) will be provided in PFSs.

The study treatment solution **must** be injected into **non-affected** areas of the skin.

Subjects will be instructed by the site staff on how to self-inject study treatment using a PFS, following the IFU. The injections will be self-administered into the appropriate site of the body (thighs, arms, abdomen), and each injection should be given at a different injection site to reduce the risk of reaction. Each new injection should be given at least one inch from the previously used site. If subject chooses the abdomen, a 2 inch area around the navel should be avoided. Investigational drug should not be injected into areas where the skin is tender, bruised, red, or hard, or where subject has scars or stretch marks.

Single PFSs will be packaged in individual boxes. The boxes containing the PFSs with study treatment solution should be kept at 2 to 8°C (36°F and 46°F) (Do Not Freeze) and protected from light. Prior to administration the boxes containing the PFSs with study treatment solution should be allowed to come to room temperature **unopened** for 15-30 minutes prior to injection. Used PFSs should be disposed immediately after use in a sharps container OR according to the regulatory needs of the respective countries.

Any PFS for which a defect or malfunction is noticed prior to or during the injection at any of the study visits, must be kept at the site until guidance is received from Novartis on whether it should be returned to Novartis for investigation or discarded. Devices identified as defective should be stored according to local guidelines, until specific instruction is discussed with Novartis personnel. Additionally, from BSL onwards, any noticed defect, malfunction, problem during the injections or product complaints with the PFS should be recorded in the source document and the Use of Device electronic case report form (eCRF). Sites should detail the issue, the date, the kit number and the visit number. Site will be asked to record based on their judgment whether the observed issue was primarily related to the device or to the user. Device malfunctions should also be immediately reported to Novartis personnel as a necessary replacement kit may need to be provided.

5.5.4.2 Home administration

Up to Week 52, all doses of study treatment will be self-administered by the subject at the study site, after the study assessments for the visit have been completed. After Week 52 the subjects will be allowed to self-administer the study treatment at home during the optional visits period when there are no scheduled site assessments. Optional site visits are included in the assessment table ([Table 6-2](#)) and during these visits trial related procedures are to be conducted. Subjects will be allowed to self-administer the study treatment via PFS at home or to visit the site during the optional visits to self-administer study treatment under the supervision of the site staff. If the subject opts for home administration of study treatment and is unable or unwilling to self-administer the treatment via PFS, a care-giver may administer the study treatment during

Treatment period 3 only. Caregivers should be trained on the IFU prior to administering the study treatment to the subject. It should be recorded on the Dose Administration Record eCRF(s) whether the subject self-administered the study treatment at home or at the site and if a caregiver administered the treatment.

Prior to self-administration at home, subjects should contact the investigator / site staff in case they are experiencing any AE/SAEs, or have any concerns.

All dates and times of self-administrations by the subject during the study must be recorded on the Dosage Administration Record eCRF. Immediately before dispensing the package to the subject, investigator staff will detach the outer part of the label from the packaging and affix it to the source document (Drug Label Form) for that subject's unique subject number.

5.5.5 Permitted dose adjustments and interruptions of study treatment

Study treatment dose adjustments are not permitted. Study treatment interruption should be avoided with the following exceptions:

Study treatment interruption is only permitted if, in the opinion of the investigator, a subject is deemed to be placed at a significant safety risk unless dosing is temporarily interrupted. In such cases study treatment should be interrupted only during the time that this risk is present and ongoing. Study treatment can be restarted at the next scheduled visit after resolution of the safety risk.

The effect of secukinumab on live vaccines is unknown; therefore live vaccines should not be administered during participation in the study. In case a live vaccine has been administered due to a medical urgency, study treatment should be interrupted for 12 weeks.

Any study treatment interruption must be recorded on the corresponding eCRF page.

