At each study treatment visit, one (for secukinumab 150 mg) or two (for secukinumab 300 mg) s.c. injections in the form of PFS will be administered, since secukinumab is available in 1.0 mL (150 mg) PFSs. Placebo to secukinumab is also available in 1.0 mL to match the active drug (see [Section 5](#)).

At Week 16, subjects who have been randomized to secukinumab groups at BSL (Groups 1-3) will be classified as either responders ($\geq 20\%$ improvement from BSL in both tender joint count (TJC) and swollen joint counts (SJC)) or non-responders ($< 20\%$ improvement from BSL TJC or SJC), however they will continue on the same treatment irrespective of their response status.

At Week 16, subjects who have been randomized to placebo at BSL (Group 4) will be classified as either responders ($\geq 20\%$ improvement from BSL in both TJC and SJC) or non-responders ($< 20\%$ improvement from BSL in TJC or SJC):

- Subjects who are **non-responders** will receive either secukinumab 150 mg or 300 mg s.c. every 4 weeks starting at Week 16 (as dictated by treatment sequence assigned to these subjects at BSL).

- Subjects who are **responders** will continue to receive placebo every 4 weeks. Starting at Week 24, these subjects will receive either secukinumab 150 mg s.c. or 300 mg s.c. every 4 weeks (as dictated by treatment sequence assigned to these subjects at BSL).

At Week 24, the assessments will be performed as described in [Table 6-1](#). As described above, subjects who are still receiving placebo s.c. injection will receive either secukinumab 150 mg s.c. or 300 mg s.c. every 4 weeks starting at Week 24 (as dictated by treatment sequence assigned to these subjects at BSL).

[figure not shown]
Beginning at Week 52, for subjects whose signs and symptoms are not well controlled, and who the investigator believes may improve further with an increase in dose, may have the secukinumab dose increased to 300 mg s.c. every 4 weeks. This will be performed in a blinded manner until after the Week 52 interim analysis database lock is performed.

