Although the number of subjects on the placebo group is higher than any of the individual secukinumab groups, when considering the ratio of secukinumab (all three groups) vs. placebo, the ratio is 2:1. This is justifiable from an ethical standpoint and the statistical justification is provided in [Section 3.1](#).

Subjects will receive treatment at BSL, Week 1, 2 and 3, followed by treatment every 4 weeks starting at Week 4. Subjects will self-administer all secukinumab and placebo doses through Week 104 (with last dose given at Week 100).

At Week 16, subjects who have been randomized to secukinumab groups at BSL (Groups 1-3) will be classified as either responders ($\geq 20\%$ improvement from BSL in both TJC and SJC) or non-responders ($< 20\%$ improvement from BSL TJC or SJC), however they will continue on the same treatment irrespective of their response status. However the non-responders, defined as subjects with $< 20\%$ improvement from BSL in TJC or SJC, and originally randomized to placebo at BSL (Group 4) will receive either secukinumab 150 mg (one injection each of secukinumab 1 mL/150 mg and 1 mL placebo for 150 mg) or secukinumab 300 mg (two injections of secukinumab 1 mL/150 mg) in a double-blinded fashion (as dictated by treatment sequence assigned to these subjects at BSL).

At Week 24, the remaining subjects originally randomized to placebo (Group 4) and who continued receiving placebo s.c. injection after Week 16 will receive secukinumab 150 mg (one injection each of secukinumab 1 mL/150 mg and 1 mL placebo for 150 mg) or secukinumab 300 mg (2 injections of secukinumab 1 mL/150 mg) in a blinded fashion (as dictated by

treatment sequence assigned to these subjects at BSL). Therefore, after Week 24, all subjects in every treatment arm will receive 2 PFS injections (either 2 x 150 mg/mL for 300 mg or 1 x 150 mg/mL of secukinumab + 1 mL placebo for 150 mg) in a blinded fashion until open-label treatment is started.

Subjects will self-administer all secukinumab and placebo doses at the study site through Week 52.

Beginning at Week 52, for subjects whose signs and symptoms are not fully controlled, and who the investigator believes may improve further with an increase in dose, may have the secukinumab dose increased to 300mg s.c. every 4 weeks. This will be performed in a blinded manner until after the Week 52 interim analysis database lock is performed.

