## **2.2 Analysis sets and treatment groups**

The following analysis sets will be used for the data analysis.

**Randomized set:** The randomized set will be defined as all subjects who were randomized. Unless otherwise specified, mis-randomized subjects (mis-randomized in Interactive Voice Response (IVR)) will be excluded from the randomized set.

Mis-randomized subjects are defined as those subjects who were mistakenly randomized into the IVR prior to the site confirming all eligibility criteria had been met and to whom no study medication was given. Mis-randomized patients are treated as screen failures.

**Full analysis set (FAS):** The FAS will be comprised of all subjects from the randomized set to whom study treatment has been assigned. Following the intent-to-treat principle, subjects will be analyzed according to the treatment assigned to at randomization, but actual anti-TNF status.

**Dactylitis subset:** The dactylitis subset will include all FAS subjects who have dactylitis at baseline.

**Enthesitis subset:** The enthesitis subset will include all FAS subjects who have enthesitis at baseline.

**Psoriasis subset:** The psoriasis subset will include all FAS subject who have  $\geq 3\%$  of the body surface area (BSA) affected by psoriatic skin involvement at baseline.

**Nail subset:** The nail subset will include all FAS subject who have psoriasis currently in nails at baseline.

**Up-titration subset:** Up-titration subset will include all FAS subjects who have been up-titrated to secukinumab 300mg in the second year of the study.

**Safety set:** The safety set includes all subjects who took at least one dose of study treatment during the treatment period. Subjects will be evaluated according to treatment received.

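### Protocol 5.5.5 bars dose adjustments without exception, while the summary, 3.1 and 5.2 allow escalation from Week 52, under a condition worded two ways

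*Protocol*

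**What the plan says.** Protocol 5.5.5, the section on permitted dose adjustments and interruptions, opens with "Study treatment dose adjustments are not permitted". The next sentence reads "Study treatment interruption should be avoided with the following exceptions", and what follows deals with interruption for a safety risk and after a live vaccine. No exception is attached to dose adjustment, and the section does not refer to 3.1 or 5.2.

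Three other current places provide for a dose increase beginning at Week 52:

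- Protocol 3.1: a subject "may have the secukinumab dose increased to 300 mg s.c. every 4 weeks". The condition is "for subjects whose signs and symptoms are not well controlled".
- Protocol 5.2: a subject "may have the secukinumab dose increased to 300mg s.c. every 4 weeks". The condition is "for subjects whose signs and symptoms are not fully controlled".
- Protocol summary, Study design: the same provision, with the condition worded as in 5.2.

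All three add that the investigator must believe a higher dose may bring further improvement. All three say the increase is made blinded until after the Week 52 database lock.

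SAP 2.2 treats escalation as planned: "Up-titration subset will include all FAS subjects who have been up-titrated to secukinumab 300mg in the second year of the study". SAP 2.2.2 splits each 150 mg sequence into subjects who stay on 150 mg and subjects who are up-titrated.

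**The concern.** The section whose title announces what dose changes are permitted gives a flat prohibition, and three other sections give a permission. As written, a site cannot satisfy both.

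What is at stake is the handling of second-year dosing. Protocol section 11 requires significant deviations to be recorded and reported in the clinical study report, and SAP 2.3.1 tabulates subjects for each protocol deviation. If some sites or monitors read an escalation as a breach of 5.5.5 and others as a planned step, the same act will be classified differently, and the deviation tables will mix the two.

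The two wordings of the condition add a smaller uncertainty. Two investigators working from different sections could apply a different degree of disease control when deciding whom to escalate, which bears on who enters the up-titrated sequences.

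**Working it through.** No power, alpha or event figure is involved, so the check is a comparison of current text. It does not rely on the amendment summaries.

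**Step 1. Prohibition against permission.**

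| Place | Dose change after Week 52 | Condition |
|---|---|---|
| Protocol 5.5.5 | Not permitted; exceptions cover interruption only | None |
| Protocol summary | Increase to 300 mg allowed | Not *fully* controlled |
| Protocol 3.1 | Increase to 300 mg allowed | Not *well* controlled |
| Protocol 5.2 | Increase to 300 mg allowed | Not *fully* controlled |
| SAP 2.2, 2.2.2 | Up-titration assumed to occur | None; classified by dose given |

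A rise from 150 mg to 300 mg at the investigator's decision is a dose adjustment in the ordinary sense. Section 5.5.5 excludes none from its scope, so the first row conflicts with the next three.

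**Step 2. The two wordings.** Taken literally, *not fully controlled* is the wider condition, because a subject may be well but not fully controlled. Neither term is tied to a score, cut-off or instrument. Both sit beside the same investigator-belief condition and the same discretionary *may*. The wordings can therefore select different subjects, but the documents give no way to say how many.

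**Step 3. Upper bound on subjects whose dose could change.** Inputs are from Protocol 5.2: 220 in Arm 1 (150 mg without loading), 220 in Arm 2 (150 mg with loading) and 165 in Arm 4 (placebo, then 150 mg).

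- Assigned to 150 mg by Week 52: 220 + 220 + 165 = 605.
- Share of all randomised: 605 / 990 = 61%.
- The other 220 + 165 = 385 (Arms 3 and 5) are assigned to 300 mg already, so their dose cannot rise under this provision.
- Protocol section 4 anticipates 25% dropout in the first year. If that fell evenly across arms (an assumption), 605 × 0.75 ≈ 454 would remain.

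Both 605 and 454 count subjects who could be eligible. Neither estimates how many would be handled differently because of the conflict.

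**Step 4. Reach.** Escalation starts at Week 52. ACR20 and the other clinical endpoints are tested at Week 16 and mTSS at Week 24, so the confirmatory tests, alpha and power are untouched. SAP 2.2.2 confines the up-titration subgroup analysis to the final Week 112 database lock.

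**The case against.** The best defence is that 5.5.5 means ad hoc changes only. Escalation is set out three times with its timing, dose and blinding, and a specific provision would normally prevail over a general one. Protocol 8.3 expects dosage changes to be tracked in the IRT. Protocol 7.1 lists dosage adjustment among the responses to an adverse event, and the rest of 5.5.5 is about safety interruptions. Nor does 5.5.5 make an exception for the planned move from placebo to secukinumab at Week 16 or 24.

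Much of this stands. It makes the ad hoc reading plausible, and it is unlikely that sites would conclude that nobody may be escalated. But 5.5.5 nowhere states that limit. The comparison with the placebo switch is also imperfect: that switch follows the sequence assigned at baseline, whereas escalation departs from the assigned dose on an investigator's decision.

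Two stronger readings are tempting, and the documents do not support them.

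- A reader might infer that the two wordings are different eligibility thresholds. They are not thresholds: neither is measurable, and both leave the decision to the same judgment. Choosing one adverb removes the inconsistency but does not make selection reproducible.
- A reader might infer that the SAP's up-titration subset is ill-defined and should carry the escalation condition. It is defined by the dose actually given, which is clear under either wording. Redefining it by the condition would replace an observed fact with an undefined judgment, and could count eligible subjects who were never escalated.

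**Conclusion.** The protocol is internally inconsistent and 5.5.5 is wrong as written: taken literally, it makes a breach of every escalation that the summary, 3.1 and 5.2 provide for and the SAP plans to analyse. The difference in the wording of the condition is real but secondary.

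The practical risk is uneven deviation handling and some unevenness in who is escalated, both in the second year only. The 605 of 990 (61%) is a ceiling resting on the planned arm sizes before dropout, and should not be read as the number affected. The conclusion does not depend on which rule or wording the sponsor intended.

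**What to change.** The sponsor should reconcile 5.5.5 with the escalation text in the summary, 3.1 and 5.2, so that the four places state one rule and 5.5.5 refers to the others. The escalation condition should then carry one wording in all three places where it appears. This review takes no position on which rule or which wording is right.

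The SAP up-titration subset and the stay/up-titrated sequences should be left as they are.

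One nearby sentence is worth checking in the same pass. Protocol 3.1 and the summary say that subjects continue on the same active dose once treatment becomes open-label, which leaves unclear whether escalation is still available after that point.

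The cost is protocol wording only: no change to sample size, testing strategy or data collection.
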